11.1 DETERMINATION OF SAMPLE SIZE AND STUDY POWER

The expected mean decline in FACT-P score and within group standard deviation for the control arm treated with 12 months of LHRHa monotherapy is 4-8 and 8-12 points, respectively, based on prior studies of measuring QOL using FACT-P among men treated with ADT [32, 58, 59]. A change in total FACT score that is clinically meaningful and impacts treatment in prior studies ranges from 5-8 points depending on cancer subtype [56]. Approximately 30 subjects will be randomized to each of the 3 treatment arms for this comparison. Accounting for a dropout/questionnaire non-completion rate of 10%, this will allow for 27 evaluable subjects per study arm. For the comparison of the mean change in FACT-P score between ARN-509 monotherapy and LHRHa monotherapy, this sample size has 80% power to detect an effect size of at least 0.86, corresponding to a difference of 7.5 points in mean 12 month change in FACT-P score between treatment groups with a common standard deviation for the change in each arm of 8.7 which is similar to the reported standard deviation for LHRHa monotherapy. This is based upon a 2 group t test, using a bidirectional level of significance of 0.025 (adjusted for 2 comparisons). To test for non-inferiority in QOL with ARN-509 + LHRHa compared with LHRHa monotherapy, inferior QOL is defined as a greater than 7 point difference in mean change in FACT-P score between the treatment groups and the common standard deviation is again assumed to be 8.7. This sample size has 82% power to reject the null hypothesis of a difference in mean score and accept the alternative hypothesis of non-inferiority with an effect size of at least 0.81, using a 2 group t-test with 2-sided α of 0.025.

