5.1 Analysis Specification

5.1.1 Level of Significance

In general, a two-sided significance level of $\alpha = 0.05$ will be used for all hypothesis testing and all CIs will be calculated on the two-sided 95% confidence level, unless otherwise specified. Since this is a three-arm study testing two simultaneous hypotheses, $\alpha/2 = 0.025$ level of significance will be used to test each.

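### Testing each primary hypothesis at a fixed 0.025 is valid, but Holm's step-down would give more power within the same 0.05 family-wise bound

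*SAP*

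**What the plan says.** SAP 5.1.1 sets a general two-sided level of 0.05, which "will be used for all hypothesis testing and all CIs will be calculated on the two-sided 95% confidence level" unless otherwise specified. For the two primary hypotheses it halves this: "Since this is a three-arm study testing two simultaneous hypotheses", a 0.025 "level of significance will be used to test each".

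Protocol 11.1, repeated in SAP 1.4, uses the same split for the power calculation. Superiority of apalutamide monotherapy over LHRHa is sized "using a bidirectional level of significance of 0.025 (adjusted for 2 comparisons"). Non-inferiority of the combination is sized "using a 2 group t-test with 2-sided α of 0.025", with a 7-point margin and a stated power of 82%.

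The primary analysis sections (protocol 11.4.1, SAP 5.2.1) define the two contrasts and the margin. They contain no ordering, hierarchy or transfer of alpha, and they give no interval level for the primary contrasts.

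**The concern.** Under the fixed split, rejecting one primary hypothesis does not help the other, which is still tested at 0.025. Once one of two hypotheses has been rejected at 0.025, Holm's procedure allows the other to be tested at the full 0.05 without exceeding 0.05 family-wise. The present plan leaves that alpha unused.

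The trial is small (about 30 randomized per arm), and the stated power for superiority is only 80%. Both questions are primary objectives, and each is meant to support its own line of further study. What is at stake is a few points of power on each question and about ten points on answering both, with no added patients.

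**Working it through.** **Inputs.** From protocol 11.1 and SAP 1.4: 27 evaluable per arm; difference 7.5; SD of change 8.7; margin 7; 0.025 per hypothesis. From the design: 1:1:1 allocation with a shared LHRHa control. My assumption, not stated in the documents: a true non-inferiority difference of 0. Two-group t tests are used, as in the plan's own power calculation; the planned analysis is a repeated-measures model.

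**1. The plan's own figures.** The standard error of a difference is 8.7 × √(2/27) = 2.368, with 52 degrees of freedom. The critical value is 2.308 at one-sided 0.0125 and 2.007 at one-sided 0.025. Power comes from the noncentral t.

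- Superiority: noncentrality 7.5/2.368 = 3.167. At two-sided 0.025, power is 80.2%. The stated 80% reproduces.
- Non-inferiority: noncentrality 7/2.368 = 2.956. At two-sided 0.025 (one-sided 0.0125), power is 74.0%, not the stated 82%. At one-sided 0.025 it is 82.7%.

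Both readings of the non-inferiority test are therefore carried below.

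**2. The rules compared.** Let p1 be the two-sided superiority p-value. Let p2 be the non-inferiority p-value against −7: twice the one-sided value under the two-sided reading, or the one-sided value itself under the other.

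- Fixed split: reject each hypothesis if its p ≤ 0.025.
- Holm: reject the smaller p if ≤ 0.025; if rejected, reject the other if ≤ 0.05.

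Holm's first step is the Bonferroni test. It therefore rejects everything the fixed split rejects and sometimes more. Its 0.05 bound needs no assumption about the correlation that the shared control creates.

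**3. Power at the design alternative** (1,000,000 simulated three-arm trials per scenario):

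| | Two-sided 0.025 as written: fixed → Holm | Non-inferiority at one-sided 0.025: fixed → Holm |
|---|---|---|
| Superiority | 80.2% → 84.4% | 80.2% → 85.2% |
| Non-inferiority | 74.0% → 80.1% | 82.7% → 87.2% |
| Both | 64.6% → 74.8% | 70.6% → 80.3% |
| At least one | 89.7% → 89.7% | 92.2% → 92.2% |

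The plan cites SDs of 8 to 12 for the control arm. Under the reading as written, power for both goes from 74.5% to 83.0% at SD 8, and from 30.2% to 40.7% at SD 12.

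**4. Family-wise error** (two-sided for superiority):

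| | As written: fixed → Holm | One-sided 0.025: fixed → Holm |
|---|---|---|
| Both nulls true | 0.036 → 0.036 | 0.047 → 0.047 |
| Only superiority null true | 0.025 → 0.042 | 0.025 → 0.043 |
| Only non-inferiority null true | 0.013 → 0.025 | 0.025 → 0.049 |

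The 0.05 bound holds throughout. Actual error rises when exactly one null is true.

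**5. Why the scale matters.** Suppose a raw one-sided non-inferiority p of 0.020 (threshold 0.0125) were ordered against a two-sided superiority p of 0.024 (threshold 0.025). The smaller p, 0.020, fails its threshold and testing stops. The present plan would have rejected superiority. At the design alternative such unscaled ordering loses about 0.5% of trials, and the rule is then no longer uniformly better.

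**The case against.** The strongest case against the point is that nothing here is wrong. Bonferroni is valid, prespecified, consistent between protocol and SAP, and the basis of the superiority sample size. That stands. A reader might infer that the plan fails to control error or that the sample size must change. The documents support neither.

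A reader might also take the 65% to 75% line as the trial's power. No passage requires both hypotheses to succeed. They are stated separately, and the study rationale treats a favorable result for either strategy as enough to justify larger trials. On at least one success Holm gains nothing. The gain that applies to each question is 4 to 6 points.

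Nor is the gain free. The bound is unchanged, but false superiority rises from 2.5% to about 4.2% when only that null is true.

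Holm also breaks the match between test and simple interval. Under the reading as written, in about 6% of trials (80.1% − 74.0%) it would declare non-inferiority while the 97.5% interval crosses −7. A fixed split keeps the two together. This matters for a conclusion based on a margin and has to be handled in the wording.

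Finally, the trial is open-label, and the protocol abstract records that the last patient has been consented. Relaxing a primary threshold at this stage needs a stated justification and must precede database lock.

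**Conclusion.** The point holds as a missed efficiency. Within the same 0.05 family-wise bound, Holm adds about 4 to 5 points of power for superiority, 5 to 6 for non-inferiority and 10 for both, and none for at least one. These figures rest on the plan's 27 per arm, SD 8.7, difference 7.5 and margin 7, on t tests, and on an assumed true non-inferiority difference of 0.

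The 74% non-inferiority baseline follows from reading the stated two-sided 0.025 literally; the plan itself states 82%, which only a one-sided 0.025 test comes close to. The direction and rough size of the gain are the same on either reading, but the rule cannot be written until the reading is chosen. The change is worth making because it is cheap. Keeping the fixed split would not invalidate the trial.

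**What to change.** Amend SAP 5.1.1 before database lock, with matching notes in SAP 1.4 and protocol 11.1:

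1. State whether the non-inferiority test is two-sided 0.025 (one-sided 0.0125) or one-sided 0.025, and make the stated power agree.
2. Put both p-values on one scale. Under the two-sided reading, use the two-sided superiority p and twice the one-sided non-inferiority p against −7.
3. Test the smaller at 0.025. If it is significant, test the other at 0.05; otherwise stop.
4. State that the Holm test decides. Report 97.5% intervals for both primary contrasts, plus the 95% interval for a hypothesis tested at the second step so that interval and decision agree. If the one-sided reading is chosen, the matching two-sided intervals for non-inferiority are 95% at the first step and 90% at the second.
5. Record the reason for the change and that it was made without reference to outcome data by arm.

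The cost is wording and a short justification. Sample size, visits, data collection and the primary model are unaffected. The price is actual error closer to the 0.05 bound and no simple simultaneous intervals that match the decision exactly.

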5.1.2 Data Handling Rules

In general, no imputation method is planned for handling missing or incomplete data. Sensitivity analyses with censoring rules may be conducted if warranted and will be documented in the clinical study report.

5.2 Primary Endpoint

The primary efficacy endpoint is the mean change from baseline in total FACT-P score at 12 months. The FACT-P scale is described in section 5.4.1.

5.2.1 Analytic Plan for the Primary Endpoint

Change from baseline in FACT-P total scale will be analyzed using a mixed-model for repeated measures. The model will include baseline scale, treatment, month (categorical), and treatment-by-month interaction as covariates. An unstructured variance-covariance matrix will be used to model within-subject errors, but simpler structures (eg, compound symmetry) may be used to ensure estimation convergence. Change from baseline will be estimated using least-squares means with factor levels weighted according to overall baseline sample means. Data up to 12 months will be included in the analysis and the primary time point of interest will be at 12 months. Contrasts will be set up to compare apalutamide monotherapy vs. LHRHa monotherapy and apalutamide + LHRHa vs. LHRHa monotherapy. To test for non-inferiority with respect to apalutamide + LHRHa compared with LHRHa monotherapy, inferior boundary is defined as a greater than 7-point difference in mean change in FACT-P total score. The estimated least-squares mean (+/- SE) over time will be presented using a line plot. A sensitivity analysis will be conducted by including data up to 24 months.

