11.4.2 Analytic Plan for the Secondary Endpoints

The secondary QOL endpoints will be analyzed using a similar approach as for the primary endpoint. Data up to 24 months will be included in the analysis.

PSA Modulation:

The proportion of subjects without PSA or radiographic progression and who have recovered serum testosterone to greater than 150 ng/dL at 24 months from Day 1 will be compared for subjects treated ARN-509 monotherapy vs. LHRHa monotherapy and for ARN-509 + LHRHa vs. LHRHa monotherapy. The proportions by treatment will be compared using the chi-square test or Fisher's exact test as appropriate. Results will be summarized at 24 months from Day 1 with 95% confidence intervals for each treatment arm. Subjects who withdraw from the study prior to 24 months after Day 1 will not be included in this analysis. Details can be found in the statistical analysis plan (SAP).

The proportion of subjects with a PSA less than 0.2 ng/mL after 7 months of protocol therapy will be analyzed using similar approaches for proportion of subjects without evidence of PSA or

radiographic progression during the 24-month treatment period and with recovery of serum testosterone at 24 months.

The probability distributions by treatment group of the time to PSA progression will be estimated using the Kaplan-Meier method. Durations will be measured from Day 1 of study treatment to the first date of PSA progression. The log-rank test will be used to compare the distribution of time to PSA progression.

Metabolic and Hormonal Parameters:

The mean change from baseline for markers of insulin resistance (including fasting glucose, insulin, body mass index, and hemoglobin A1C), fasting lipid panel (including total cholesterol, LDL, HDL, and serum triglycerides), and hormone levels (including DHT and estradiol) analyzed using a similar approach as for the primary endpoint.

The mean change in bone mineral density at the femoral neck, and lumbar spine as measured by DEXA scan will be compared for ARN-509 monotherapy vs. LHRHa monotherapy and ARN-509 + LHRHa vs. LHRHa monotherapy using an analysis of covariance (ANCOVA) that controls for baseline values of the corresponding measurement.

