1.5 Randomization and Blinding

1.5.1 Randomization

Upon verification of inclusion and exclusion criteria, eligible patients will be centrally randomized in a 1:1:1 ratio to apalutamide monotherapy, apalutamide + LHRHa, or LHRHa monotherapy. The randomization will be stratified as follows:

- PSADT (< 6 months vs. 6-12 months)
- Age at study entry (≤ 70 years vs. > 70 years)

Balance in treatment assignment will be achieved using a randomized block design. Randomization will be carried out via computer generated random assignment. All subjects must commence treatment within (5 calendar days) of randomization. Study sites will email the Eligibility Checklist to the sponsor to obtain the subject's treatment assignment. Once subject eligibility is confirmed by the sponsor, an email with the treatment assignment number will be provided to the study site.

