5. EFFICACY

This section outlines the planned analyses of the primary, secondary, and other efficacy endpoints of the study.

Efficacy analyses will be performed in the ITT population, incorporating the randomization stratification factors. All continuous variables will be summarized using number of subjects (n), mean, standard deviation (SD), median, minimum, and maximum. Categorical variables will be summarized with count and percentage.

Time-to-event endpoints will be summarized using the Kaplan-Meier method [6] and displayed graphically where appropriate. Median event times and two-sided 95% confidence interval (CI) for each treatment group will be provided. Stratified Cox proportional-hazard models will be used to estimate the hazard ratio (HR) and its 95% CI. The stratification factors to be used in the analysis are PSADT (< 6 months vs. 6-12 months), and age at study entry (≤ 70 years vs. > 70 years).

The testing for the time-to-event endpoints will be based on the stratified log rank test; non-stratified log rank test will be performed as a sensitivity analysis, as appropriate. Multivariate Cox regression analysis, adjusting for important selected prognostic factors.

The proportional hazard assumption will be assessed graphically by plotting log (-log [estimated survival distribution function]) against log (survival time). The resulting graphs should have approximately parallel lines when the assumption holds. If the proportional hazards assumption is reasonably met, then the HR will be used as an estimate of treatment effect. If the proportional hazards assumption is violated, then the inference remains statistically valid for testing equality in survival distributions, but treatment effect will only be estimated using the median time to event in each treatment group.

Endpoints with binary outcome will be summarized by descriptive statistics (count and percentage) by the treatment group. The risk ratio or risk difference (treatment: control) will be reported along with the corresponding two-sided 95% CI. The two treatment groups will be compared by using the chi-square test; Fisher's exact test may be used if the expected counts in some of the cells are less than 5.

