5.3.1 Analytic Plan for the Secondary Endpoints

5.3.1.1 Quality of Life

The secondary QOL endpoints will be analyzed using a mixed-model for repeated measures like the primary endpoint. The model will include baseline scale, treatment, month (categorical), and treatment-by-month interaction as covariates. FACT-P, EORTC QLQ-C30/PR25, and SHIM scales are described in sections 5.4.1, 5.4.2, and 5.4.3, respectively.

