5.3.1.3 Metabolic and Hormonal Parameters

The mean change from baseline for markers of insulin resistance (including fasting glucose, insulin, body mass index, and hemoglobin A1C), fasting lipid panel (including total cholesterol, LDL, HDL, and serum triglycerides), and hormone levels (including DHT and estradiol) analyzed using a similar approach as for the primary endpoint.

The mean change in bone mineral density at the femoral neck, and lumbar spine as measured by DEXA scan will be compared for apalutamide monotherapy vs. LHRHa monotherapy and apalutamide + LHRHa vs. LHRHa monotherapy using an analysis of covariance that controls for baseline values of the corresponding measurement.

The time to serum testosterone recovery to > 50 ng/dL and > 150 ng/dL after the cessation of protocol therapy at 12 months will be compared for apalutamide + LHRHa vs. LHRHa monotherapy. The probability distributions by treatment group of the time to testosterone recovery will be estimated using the Kaplan-Meier method. The log-rank test will be used to compare the distribution of time to testosterone recovery. Subjects who discontinue study drug prior to 12 months for disease progression, unacceptable toxicity, or study withdrawal, as well as subjects who continue hormonal therapy after 12 months or receive non-protocol therapy, will not be included in the analysis of this exploratory endpoint.

No adjustment for multiple comparisons will be made for the analysis of the secondary and correlative endpoints.

Table 1: Key censoring rules

Scenario	Censoring rule
Time to PSA Progression	
 Any increase in PSA to $> 50\%$ of the baseline value or an increase of ≥ 2 ng/mL above the nadir, whichever is higher, and confirmed by repeat measurement at least 2 weeks later is considered an event. Subjects who have no PSA progression at the time of analysis will be censored at the last known date of PSA assessment. Subjects without a baseline PSA or without any post baseline values will be censored at randomization date.

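### SAP Section 5 says efficacy analyses use the randomisation strata, but the FACT-P and other MMRMs and the BMD ANCOVA leave out both PSADT and age

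*SAP*

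**What the plan says.** SAP 1.5.1 stratifies a 1:1:1 randomisation by PSADT (<6 vs 6-12 months) and age (<=70 vs >70 years): "Balance in treatment assignment will be achieved using a randomized block design".

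SAP Section 5 opens with a general statement: "Efficacy analyses will be performed in the ITT population, incorporating the randomization stratification factors". It then names PSADT and age as the analysis factors in its time-to-event paragraph. SAP 5.2 places FACT-P within the scope of efficacy: "The primary efficacy endpoint is the mean change from baseline in total FACT-P score at 12 months".

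The model specifications are narrower:

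- **Primary FACT-P MMRM (SAP 5.2.1, and the same list in Protocol 11.4.1):** "The model will include baseline scale, treatment, month (categorical), and treatment-by-month interaction as covariates".
- **Secondary QOL (SAP 5.3.1.1):** "The secondary QOL endpoints will be analyzed using a mixed-model for repeated measures like the primary endpoint", followed by the same four terms.
- **Metabolic and hormonal markers (SAP 5.3.1.3):** "analyzed using a similar approach as for the primary endpoint".
- **BMD at femoral neck and lumbar spine (SAP 5.3.1.3):** "using an analysis of covariance that controls for baseline values of the corresponding measurement". Protocol 11.4.2 agrees: "using an analysis of covariance (ANCOVA) that controls for baseline values of the corresponding measurement".

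Neither document exempts these models from the Section 5 statement. The protocol's analysis section has no equivalent general sentence, so the inconsistency lies within the SAP.

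**The concern.** A programmer following 5.2.1 fits a model without strata; one following Section 5 adds them. SAP Section 1 requires departures from the plan to be described in the study report, and either choice departs from one SAP sentence.

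The statistical stake is precision. Blocking within strata balances the arms on PSADT and age, which lowers the true sampling variance of the treatment contrast if those factors predict the outcome. A model without the factors leaves their variance in the residual. Its standard error is then too large, the test is somewhat conservative, and the precision gained by stratifying is not fully used. With 27 evaluable men per arm and power planned at only 80%, a gain that costs almost nothing is worth taking.

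No conflict arises for the binary endpoints, because Section 5 itself assigns them chi-square or Fisher tests.

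**Working it through.** **Inputs from the documents (SAP 1.4):** 27 evaluable per arm (30 less 10%), SD of change 8.7, difference 7.5 points, two-sided level 0.025 per comparison, two-group t test.

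**The plan's own figure.** Standard error = 8.7 x sqrt(2/27) = 2.368. Noncentrality = 7.5/2.368 = 3.17. The noncentral t with 52 df gives power 80.2%, which reproduces the stated 80%. That figure assumes no covariates, so omitting the strata does not take power below it.

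**Assumed, because the documents do not give them:** the share of change variance explained by baseline (0, 0.10, 0.25) and the partial R2 of the two strata after baseline (0, 0.02, 0.05, 0.10). Block size 6, equal stratum prevalence and equal effects of the two factors are also assumptions.

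**Closed form.** Residual SD = 8.7 x sqrt(1 - R2). The 81 evaluable men leave 81 - 3 - 1 = 77 error df without strata and 75 with two stratum terms. At R2 = 0.10 the SD is 8.25, the standard error 2.246 and the noncentrality 3.34.

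| | No strata | Strata, R2 = 0 | 0.02 | 0.05 | 0.10 |
|---|---|---|---|---|---|
| Superiority power, % | 80.9 | 80.9 | 81.7 | 83.0 | 85.1 |
| Non-inferiority power (margin 7, one-sided 0.0125), % | 74.7 | 74.7 | 75.6 | 77.1 | 79.5 |

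At R2 = 0 the superiority cost is 0.04 point on these df, or about 0.1 point on two-group df (52 vs 50). The closed form somewhat overstates the gain, because it gives the model without strata no credit for the balance already achieved by blocking. Simulation does give that credit.

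**Simulation.** 90 men were randomised in permuted blocks within four strata, with 81 evaluable. Month-12 change was regressed on arm and baseline, with and without the two strata; 20,000 trials per cell. Superiority power in %, without vs with strata:

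| Baseline share | R2 = 0 | 0.02 | 0.05 | 0.10 |
|---|---|---|---|---|
| 0 | 80.4 vs 79.9 | 80.6 vs 81.0 | 81.0 vs 82.4 | 81.2 vs 84.6 |
| 0.10 | 84.7 vs 84.5 | 85.2 vs 85.6 | 85.1 vs 86.5 | 85.8 vs 88.3 |
| 0.25 | 90.9 vs 90.8 | 90.8 vs 91.2 | 91.5 vs 92.4 | 91.6 vs 93.3 |

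Differencing the table entries gives a loss of 0.1 to 0.5 point at R2 = 0 and a gain of 1.7 to 3.4 points at R2 = 0.10. The Monte Carlo standard error of each power is about 0.3 point.

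Type I error at nominal 0.025, over the 12 cells:

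- without strata: 0.017 to 0.026
- with strata: 0.023 to 0.026
- rejecting if either model rejects: 0.024 to 0.028

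Picking the better-looking model after the fact would therefore gain almost nothing.

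**Checks.**

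- A full MMRM (Months 3 and 12, unstructured covariance, baseline share 0.10, residual correlation 0.5, 4,000 trials per cell) gave 85.9 vs 85.7, 86.3 vs 87.3 and 87.1 vs 89.9% at R2 = 0, 0.05 and 0.10.
- A separate ANCOVA simulation (6,000 runs, 10% missing at random) gave 79.5 vs 78.7, 80.7 vs 82.0 and 81.3 vs 84.8% at the same R2 values, and 82.2 vs 88.9% at R2 = 0.20. Without strata at R2 = 0.10, the reported standard error averaged 2.38 against an actual 2.28, which is the conservatism described above.

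**BMD.** Protocol 1.5.2.2 cites a 12-month change of 1.9 +/- 2.7% at the proximal femur. Reading 2.7 as an SD and assuming 27 per arm, the 95% half-width without strata is t(0.975, 77) x 2.7 x sqrt(2/27) = 1.46 percentage points. With strata (75 df) it is 1.46, 1.45, 1.43 and 1.39 at R2 = 0, 0.02, 0.05 and 0.10.

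**The case against.** The strongest reply is that specific text governs general text. Section 5 names the factors only beside the stratified Cox model, gives binary endpoints unstratified tests, and so does not apply its opening sentence everywhere. The SAP and protocol also agree word for word on the MMRM terms. This is a reasonable reading, but the SAP states no order of precedence, and the opening sentence comes before the time-to-event paragraph and covers efficacy analyses generally.

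The opposite reading is that the term list is not exhaustive. SAP 5.2.1 weights its least-squares means by the observed baseline mix of factor levels, which has little to act on if treatment and month are the only factors. That clause may be boilerplate or a sign that strata were intended. If it was intended, the strata belong in the list.

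Three limits stand:

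- The benefit rests entirely on an assumed R2. Protocol 6.1 justifies the strata by time to progression and testosterone recovery, not by FACT-P.
- Absence of bias was shown with missingness unrelated to arm and stratum. In a deliberately extreme case (3% vs 17% missing by stratum, reversed between arms), omitting the strata biased the estimate by 0.2 to 0.4 point for R2 of 0.05 to 0.20, against a 7-point margin.
- The BMD illustration borrows a proximal-femur SD for femoral-neck and lumbar-spine endpoints.

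**Conclusion.** The inconsistency is real and minor. The QOL, metabolic and hormonal MMRMs and the BMD ANCOVA do not implement the Section 5 statement. Omission does not inflate type I error and leaves the planned power intact. It makes the tests slightly conservative and gives up precision only to the extent that PSADT and age predict change beyond baseline.

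For partial R2 up to 0.10, adding the strata is worth at most about 3.5 points of superiority power across the simulations. If the strata predict nothing, it costs 0.1 to 0.5 point in the main simulation and 0.8 in the smaller one, against 0.1 or less in closed form. A larger gain would need an R2 near 0.20, for which the documents give no support. Confidence is high on the text and on the direction of the effect; the size depends on the assumed R2.

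**What to change.** In SAP 5.2.1 and 5.3.1.1, add PSADT stratum (<6 vs 6-12 months) and age stratum (<=70 vs >70) to the MMRM as fixed effects; the metabolic and hormonal models then inherit them. Add the same two terms to the BMD ANCOVA in 5.3.1.3. Include one sentence recording the departure from Protocol 11.4.1 and 11.4.2.

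If the sponsor prefers the protocol's term lists, limit the Section 5 sentence to the time-to-event endpoints. That also resolves the inconsistency and needs no departure from the protocol, but it gives up the possible gain.

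As wording only, call the log-rank test stratified in 5.3.1.2 and 5.3.1.3, to match Section 5. Leave the chi-square and Fisher tests unchanged.

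The cost is a few lines of text and about two model degrees of freedom. No new data are needed, since both factors are recorded at randomisation.
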